## STUDY INFORMATION

### 1.0 Study Summary\*

### 2.0 Objectives\*

#### 2.1 Purpose, specific aims or objectives: *Describe the purpose, specific aims, or objectives. If more than one objective be sure to list separately.*

This is a post-market study to provide breast pumps to residents at a pediatric academic medical center as an additional layer of support in reaching lactation goals. Residents that do not have flexible break times and/or reliable close and secure pumping space face barriers to reaching their lactation goals. Wearable pumps provide users autonomy and flexibility regarding their pumping schedules. These devices are not covered as a "free" breast pump through most insurance companies and, while discounted, are often still at a higher price point for most new parents. By providing these for free to users, we expect to see the institutions' metrics regarding duration of pumping and satisfaction with meeting goals will be higher than national metrics. In partnership with Willow, our institution will provide free pumps to individuals as part of a study including participant consent.

Among medical residents and fellows during the study window of 3 years (one year providing devices and up to three years collecting data, tracking users through end of pumping experience), who have delivered a baby. Does access to a wearable Willow pump improve lactation experience and meeting goals regarding duration of pumping/providing milk?

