#### 2.2 Hypothesis: *State the hypotheses to be tested.*

Using a wearable breast pump will allow working mothers to continue in their professional obligations and reach their pumping goal.

Secondary: Working mothers' burnout will not increase during the use of wearable breast pump.

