include decreased risk for cancers (breast, ovary, endometrial, thyroid), type 2 diabetes, osteoporosis, cardiovascular disease, high blood pressure, and high cholesterol. Successful long-term lactation for working parents includes pumping 2-3x per day to maintain milk production and creating a supply for the infant to consume when away from the providing parent.

Even with this research and education during pre- and post-natal visits with the healthcare team, it can be difficult to balance lactation, returning to work, and creating a pumping schedule. A recent study showed that Hispanic (48.4%), Black (35%), Native American (37.3%), White (52.3%) or Asian (71%) mothers stop lactation by six months. With more women in the workplace than ever before, returning to work after a birth is extremely common and employers must work to create welcoming environments for new parents.

Healthy People 2030 has set the goal that 42.4% of infants in the United States are provided human milk exclusively for the first six months, but as of 2020 only 25.4% of infants have reached this milestone. The Center for Disease Control and Prevention (CDC) data reported from the National Immunization Survey reports that nationally 58.2% of infants receive “any milk” through 6 months of life and in Kansas, this rate is 61.6%. While many parents set a goal of six months, there is a wide range of individual goals that new mothers may set based on circumstances. One of the questions asked in this study is intent vs. actual pumping goal since this is another area that has not been explored. According to the CDC, 60% of mothers do not reach their lactation goal. In a 2012 study conducted by the San Diego Breastfeeding Center, researchers discovered that 85% of the parents in their cohort intended to pump for 3 or more months but only 32.4% met their intended goal. These data reinforce the fact that providing human milk exclusively while returning to work is a monumental task that requires resources, commitment, and support.

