**24.0 Provisions to Protect the Privacy Interests of Participants\***

**24.1** *Describe the steps that will be taken to protect participant's privacy during recruitment and while obtaining permission/assent/consent. For example, best practice is to obtain permission/assent/consent in a separate area where a private conversation can be had. If this is not possible, be sure to explain what steps will be taken to provide as much privacy as possible.*

Participants will be deidentified in the survey using a assigned study ID.

This study ID will allow us to link their survey data and their serial number of the Willow Go pump to match data from the surveys to the data from Willow. To protect anonymity, individual data for the post survey will be reviewed to ensure there are not any serious triggers in the final comments that would indicate concerns with the program, but the data reviewed cumulatively and as deidentified.

**24.2** *Describe what steps you will take to make the participant feel at ease with the research situation in terms of the questions being asked and the procedures being performed. "At ease" does not refer to physical discomfort, but the sense of intrusiveness a participant might experience in response to questions, examinations, and procedures.*

Surveys will be completed via RedCap. Individuals that reach out to participate will be provided information on pumping with the Willows and

the informed consent form at the beginning. Participants do not have to answer any questions they do not feel comfortable.

**24.3** *Indicate how the research team is permitted to access any sources of information about the participants and how the research team will protect the confidentiality of the data.*

Biographic data will be collected through the RedCap survey. And only collected at planned intervals (quarterly) to assess midpoint measurements as deidentified combined and/or aggregate data.

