## 28.0 Statistical Analysis\*

**28.1** *Describe the data analysis plan, including any statistical procedures or power analysis.*

We plan to examine changes in professional fulfillment and burnout using repeated measures t-test. We also plan to utilize descriptives and qualitative comments to show evidence of whether the Willow device helps the participant reach their lactation goals.

**28.2** *Describe how the sample size for the study was determined (e.g. formal sample size calculation, convenience sampling). To minimize the risks associated with a possible breach of confidentiality, appropriate sample size calculations limit the amount of patient data being recorded to the amount necessary to answer the research question.*

For all the planned analyses, having a study sample of 125-150 will be sufficient. This presents the goal for each site to have 20-25 participants over the next two years.

•
---

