**N/A**

**31.1** *In addition to the Principal Investigator, which individual or group will be responsible for monitoring the data and safety for this study?*

- Sponsor or Sponsor Designee (including the Sponsor CRO)
- Data and Safety Monitoring Board (DSMB) or Data Safety Monitoring Committee (DSMC)
- Independent Monitor (s)
- Internal Committee at CM
- Other: \_\_\_\_\_

**31.2 Data Safety Monitoring Plan:** *If a DSMB charter or other external monitoring plan is available, upload in the myIRB application, Other Attachments section. If such a charter/plan is not available, describe:*

- *The plan to periodically evaluate the data collected regarding both harms and benefits to determine whether participants remain safe. The plan might include establishing a data monitoring committee and reporting data monitoring committee findings to the IRB and the sponsor. For NIH funded research, see requirements for [Data and Safety Monitoring](#)*
- *What data are reviewed, including safety data, untoward events, and efficacy data.*
- *How the safety information will be collected (e.g. with case report forms, at study visits, by telephone calls with participants).*
- *The frequency of data collection, including when safety data collection starts.*
- *Who will review the data.*
- *The frequency or periodicity of review of cumulative data.*
- *The statistical tests for analyzing the safety data to determine whether harm is occurring.*
- *Any conditions that trigger an immediate suspension of the research.*

*Participation is fully voluntary and there will be no undue influence to pump if a participant is unhappy or unable to use the devices, individuals will need to let us know when they are done so Investigators can send them the final survey and remove them from the monthly send. Our survey will ask questions about what made them*

*stop pumping and there is an open text box for those that would like to provide any detail about their experience.*

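### Goal attainment, the primary question, has no named interval, test or decision rule, although the protocol expects results above national figures

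*Protocol*

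**What the plan says.** Section 2.1 expects the institution's "metrics regarding duration of pumping and satisfaction with meeting goals will be higher than national metrics". No margin is given.

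Section 2.2 makes goal attainment the main hypothesis: "Using a wearable breast pump will allow working mothers to continue in their professional obligations and reach their pumping goal". Burnout is the secondary hypothesis.

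Section 28.1 is the protocol's entire description of the analysis. It has two sentences. The first is "We plan to examine changes in professional fulfillment and burnout using repeated measures t-test". The second is "We also plan to utilize descriptives and qualitative comments to show evidence of whether the Willow device helps the participant reach their lactation goals".

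Possible benchmarks appear only in the background, section 3.3. One is the statement that "60% of mothers do not reach their lactation goal", which implies that 40% do. Another is that 58.2% of infants nationally receive any milk through 6 months. Section 28.1 refers to neither.

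Answers are optional. Section 24.2 says "Participants do not have to answer any questions they do not feel comfortable", and section 31.2 says "there is an open text box for those that would like to provide any detail about their experience".

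**The concern.** The only inferential method in the protocol serves the secondary hypothesis and a related outcome. The primary question is answered by description and comments, yet the result is to count as evidence of whether the device helps. Section 2.1 sets national figures as the yardstick, and no other analysis is assigned to that comparison.

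A bare percentage beside a fixed national figure does not separate a real excess from a chance one. Section 5.1 sends the results to the pump manufacturer, to a conference and to journals, so the word *higher* will be read as a finding. If participants did no better than the national figure, the hoped-for statement could still be made on close to an even chance.

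**Working it through.** **The plan's own figure.** Section 28.2 calls 125 to 150 participants sufficient for all planned analyses, with 20 to 25 per site. This cannot be reproduced, because no significance level, power, effect size or precision target is given. The sizes are used below as they stand.

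**Inputs.** Benchmarks p0 = 1 − 0.60 = 0.40 and p0 = 0.582 (section 3.3). n = 20, 25, 125, 150 (section 28.2). A two-sided 5% level is my assumption.

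**Step 1: bare comparison when there is no true difference.** With X ~ Binomial(n, p0), the chance of an observed rate above the benchmark is P(X > n·p0). For n = 25 and p0 = 0.40, n·p0 = 10, so the chance is P(X ≥ 11) = 0.414.

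| n | p0 = 0.40 | p0 = 0.582 |
|---|---|---|
| 20 | 0.40 | 0.53 |
| 25 | 0.41 | 0.51 |
| 125 | 0.46 | 0.52 |
| 150 | 0.46 | 0.49 |

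The chance does not fall as n grows.

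**Step 2: sampling error.** The approximate 95% half-width at p0 = 0.40 is 1.96·√(0.40·0.60/n). That is 21.5 points at n = 20, 19.2 at 25, 8.6 at 125 and 7.8 at 150. As an example, 15/25 = 60% lies 20 points above 40%, but its exact (Clopper-Pearson) 95% interval is 38.7 to 78.9%, which still includes 40%.

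**Step 3: exact rule.** Call the result higher only if the Clopper-Pearson lower 95% limit exceeds p0. For p0 = 0.40:

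| n | Smallest count that qualifies | False claim rate if true rate is 40% | Power if true rate is 50% | Power if true rate is 75% |
|---|---|---|---|---|
| 20 | 13 (65%) | 2.1% | 0.13 | 0.90 |
| 25 | 16 (64%) | 1.3% | 0.11 | 0.93 |
| 125 | 62 (49.6%) | 1.9% | 0.57 | >0.99 |
| 150 | 73 (48.7%) | 1.9% | 0.66 | >0.99 |

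The 75% is the share of users in the earlier wearable-pump programme who met or exceeded their goal, as reported in the 2025 literature update. The 50% is an assumed modest benefit.

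For p0 = 0.582 the thresholds are 17/20, 20/25, 84/125 and 100/150. The false claim rates are 1.1%, 1.9%, 2.5% and 2.1%. Power at an assumed true 70% is 0.11, 0.19, 0.78 and 0.84.

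**Step 4: when the true rate is not the benchmark.** Under the bare comparison with p0 = 0.40, a true rate of 35% shows as higher 24% of the time at n = 20 and 9% at n = 150. A true rate of 55% does so 87% of the time at n = 20 and more than 99% at n = 150.

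**The case against.** The protocol does not exclude confidence intervals. Descriptive statistics can include them, section 29.1 assigns the analysis to a biostatistical partner, and a statistical analysis plan that is not shown may supply the detail. This stands: a reader might infer that results will be reported without any measure of uncertainty, and the document does not say so. What remains is that 28.1 does state how the primary question will be answered, and the stated means include nothing that limits a chance claim.

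The comparison rule is also partly inferred. Section 2.1 states an expectation, section 2.2 does not mention national figures, and 28.1 asks only whether the device helps. Linking 2.1 to 28.1 is reasonable because no other analysis is assigned to the expectation, but the link is an inference.

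A reader might take the figure of about one half as the study's general error rate. It is not. It applies when the true rate equals the benchmark (step 4). If the true rate is near 75%, chance matters little.

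A reader might also infer that a success rate will be estimated from the comments. No section plans that. Section 5.1 lists a structured monthly item on meeting goals, and the outtake survey covers total length of pumping. The fair point is only that optional comments are listed as evidence beside the descriptives.

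Finally, the larger threat may be comparability: a single, self-enrolled group that already plans to pump (section 7.1) is set against general national figures. An interval does not address that, and this point does not claim that it does.

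**Conclusion.** The point holds in limited form. For the comparison that section 2.1 anticipates, section 28.1 names no benchmark, interval, test or decision rule, while the only named test goes to fulfillment and burnout. If the true rate equals the benchmark, a bare comparison favours the pump 41 to 52% of the time (40% and 58.2%; n = 25, 125, 150), and adding participants does not help. The exact rule brings this to 2.5% or less.

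This rests on three assumptions: that the expectation in 2.1 will be judged by the analysis in 28.1, that the benchmark is treated as a fixed number, and that the interval is two-sided 95%. The practical weight depends on the true effect: it is small near 75% against 40% and considerable near 50%. It should be fixed, but in a minimal-risk post-market survey study it is not a bar to proceeding.

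**What to change.** Add to section 28.1:

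- Goal attainment is taken from the structured survey item and reported with an exact (Clopper-Pearson) 95% confidence interval. The denominator is all participants given a pump. The number with a missing outtake survey is shown, and a sensitivity analysis counts them as not having attained the goal.
- Duration of pumping is reported with a confidence interval. Participants who leave the study while still pumping are treated as censored; sections 4.1 and 25.2 foresee such exits.
- The benchmark for each metric is named in advance. A result is called higher than the benchmark only if the lower 95% limit exceeds it.
- Comments are illustration, reported with the number commenting out of the number enrolled.

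The cost is a few sentences and no new data. The downside is that a single site of 20 to 25 may be unable to claim a higher rate, since against 40% it would need 13/20 or 16/25. The text should also say that the interval covers chance only, not the comparability of a self-enrolled group with national figures.

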### 3.0 Background\*

#### 3.1 *Describe the relevant prior experience and gaps in current knowledge.*

The relevant prior experience of the PIs includes expertise in measuring the employee experience, and 3+ years of supporting resident and fellow mothers through GME. We are conducting this study in partnership with multiple academic medical centers that include experts in lactation research and support.

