#### 3.2 *Describe any relevant preliminary data.*

Relevant preliminary data is outlined in the following literature study and experience from other institutions using a current model of a recycling program has successfully supported 70 individuals at this institution. This model will be shared with other institutions as well to create mirror projects and expand the data by providing new pumps to users. National data does not look at wearables or the impact of pumping at work specifically only breastfeeding in general, this study would fill a gap in that knowledge regarding supporting work.

**3.3** *Provide the scientific or scholarly background for, rationale for, and significance of the research based on the existing literature and how it will add to existing knowledge.*

The AAP, HP2030 and WHO lactation recommendations of six months exclusive breastfeeding up to two years of breastfeeding with table food, are based on decades of research regarding health outcomes for both the lactating parent and infant. Research shows that for the infant, the short-term benefits of lactation (described as 3 to 6 months of exclusively consuming human milk) include building important immunities against common illness in the first year of life and reducing the risk of ear infections, gastroenteritis, Respiratory Syncytial Virus (RSV), Crohn's disease, eczema, diarrhea and childhood cancers. Short-term benefits for the lactating parent include quicker recovery from giving birth, increased bonding with the infant, and lower risk of postpartum depression. Long-term lactation, described as exclusively consuming human milk for six to 24+ months, provides lifetime health benefits for the infant including lower risk of asthma, diabetes, Sudden Infant Death Syndrome (SIDS), as well as, providing important nutrition (protein, calcium, vitamin a) and enhancing brain development.

This evidence has also shown that infants who exclusively consume human milk for six months had higher IQs (intelligence quotient) compared to those who consumed human milk for less than six months. Lactation can also provide emotional support for infants as a soothing tool and physical comfort during teething. Long-term health benefits for the lactating parent

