This study will be held over the duration of one year for device distribution and remain open for up to two years or until the last participant indicated completion by completing the endpoint survey.

PI will share results with Willow at agreed upon intervals to provide good faith study data. Results will be shared in de-identified reports with the intent to present at national academic conference in conjunction with two other medical schools that are also delivering this intervention and submission for publication in academic medical journals

Drug/Device Handling: Devices stored in GME or shipped directly to individuals from Willow. No special handling needed for devices, individuals responsible for cleaning and maintenance, devices covered under warranty for first year. (*Products are covered under manufacturer 1 year warranty. All Mom's are asked to contact Willow directly for warranty/troubleshooting and exchange/replacement requests*) Please see our site for in depth warranty information <https://onewillow.com/pages/faq>. Our customer care team number to call is located here with days/times for live help and other avenues of communication to obtain live help. <https://onewillow.com/pages/contact>)

**5.2 Table of Events:** The Table of Events is another helpful tool to present the study procedures in a clear and concise manner. A Table of Events not only helps in the facilitation of IRB review, but is also a useful tool for communicating study details to study staff and even research participants. **It is highly recommended to include a Table of Events for any study involving more than one visit.**

The table below is provided as an example and may be modified as appropriate. The Table of Events must capture the procedures that will be accomplished at each study visit/interaction and all contacts with study participants e.g. telephone contacts. This includes any tests that are used for eligibility, stratification, or decisions on study intervention or discontinuation. Allowable windows should be stated for all visits.

	Intake Survey	Monthly Survey	Outtake Survey
Informed Consent	X		
Delivery of Willow	X		
Demographics	X		

	Intake Survey	Monthly Survey	Outtake Survey
Expectation for Lactation Goals	X		
Previous Lactation Experience	X		
Outcome Evaluation		X	X
Changes to Lactation Goals, practices, current volume, frequency, satisfaction, and well-being		X	X

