## SHORT TITLE: Lactation at Work

*cohort. If one of the groups includes a chart review, each chart is considered a participant and needs to be reflected in the numbers below.*

	Group 1	Group 2 (if applicable)	Totals
Enrollment Goal: Number of participants to be enrolled = the number of participants to be consented or to be screened for chart reviews.  The current rate of pregnancies in training at CMKC is approximately 20-25 per year, with the expansion of this offering we are anticipating that it will at most double. Willow has not indicated a limit on number of devices they will provide.	25 per year		25 per year

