**Is Children's Mercy (CM) acting as the single IRB of Record (sIRB)?**

**No, each site is getting their own IRB approval.**

**Yes, some or all sites will rely on the CM as the sIRB.**

- **Reliance is required for non-Exempt NIH or other Federally Funded research where:**

- *The institution's employees or agents intervene or interact with human subjects for research purposes;*
- *The institution's employees or agents obtain individually identifiable private information or identifiable biospecimens about human subjects for research purposes; or*
- *The institution receives a direct HHS award to conduct human subjects research, even where all activities involving human subjects are carried out by a subcontractor or collaborator.*

If CM is sIRB for another site, complete the chart for that site(s) (Add a new row for each site relying on the CM IRB, delete chart if not acting as sIRB):

Site Name	Enrollment Goal for Site(s) Choose One	Relying on CM IRB?
Insert Site Name	 Site Enrollment Goal: Insert #  Site will not enroll	 External Site will rely on the CM IRB as the IRB of Record using a reliance agreement. ()  Not Applicable. Site will not interact or intervene with human participants or their identifiable data / identifiable biospecimens. Site is also not a primary NIH or federal grant recipient.

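### The total of 125-150 in section 28.2 does not reconcile with the protocol's per-site goal, site count and one-year distribution window, and its sufficiency is asserted without a basis

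*Protocol*

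**What the plan says.** Section 28.2 gives the size and its justification in two sentences: "For all the planned analyses, having a study sample of 125-150 will be sufficient", and then "This presents the goal for each site to have 20-25 participants over the next two years". It gives no number of sites, effect size, standard deviation, alpha, power or allowance for loss.

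Other sections bear on the same figures:

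- **Number of sites.** Section 5.1 says results will be presented "in conjunction with two other medical schools that are also delivering this intervention". Section 3.1 says "We are conducting this study in partnership with multiple academic medical centers", without a number. Section 3.2 adds "This model will be shared with other institutions as well to create mirror projects". The site table in section 33.0 is an unfilled template ("Insert Site Name").
- **Local goal.** The table in section 8.1 sets 25 per year. It also says "The current rate of pregnancies in training at CMKC is approximately 20-25 per year" and expects that number to double at most.
- **Window.** Section 5.1 says "This study will be held over the duration of one year for device distribution and remain open for up to two years". Section 2.1 likewise allows one year for providing devices.
- **Analyses.** Section 28.1 plans a repeated measures t-test on professional fulfillment and burnout, and descriptive and qualitative summaries for lactation goals.

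**The concern.** Section 28.2 presents the total and the per-site goal as the same target expressed in two ways. They agree only if the number of sites is right, and that number is not given. With the one count that can be inferred, the two statements differ by a factor of about two. The time base is also unsettled: 25 per year in 8.1, 20-25 over two years in 28.2, and one year of device distribution in 2.1 and 5.1. Because participants receive the device at enrolment (5.1), the distribution window is in effect the accrual window.

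The size matters because 28.2 relies on it for every analysis. The one named test is a paired comparison, and the secondary hypothesis in section 2.2 is that burnout will not increase. The smaller the sample, the more easily a real increase goes undetected, so a reader needs to know which total the design is meant to deliver before interpreting a null result.

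**Working it through.** **Inputs.** Total 125-150 and 20-25 per site over two years (28.2); three sites, inferred as this institution plus two (5.1); local goal 25 per year and local pool 20-25 pregnancies per year, at most doubling (8.1); one year of device distribution (2.1, 5.1).

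**Step 1: can 125-150 be reproduced as sites x per-site goal?**

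- Three sites: 3 x 20 = 60 and 3 x 25 = 75. Against the stated range, 60/125 = 48% and 75/150 = 50%.
- Sites needed: 125/25 = 5; 125/20 = 6.25; 150/25 = 6; 150/20 = 7.5. In whole sites, that is 5 to 8.
- Six sites give 120-150, which is close, but no section mentions six.
- At three sites the total would need 125/3 = 41.7 to 150/3 = 50 participants per site.

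The literal reading with three sites does not reproduce the stated total at either end.

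**Step 2: do other readings reproduce it?**

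| Reading | Total | Conflict |
|---|---|---|
| 20-25 per site per year, two years, three sites | 120-150 | 28.2 gives 20-25 over two years; 2.1 and 5.1 allow one year of distribution |
| Doubled pool of 40-50 per site, one year, three sites | 120-150 | Needs the maximum growth in 8.1 and full uptake at every site; exceeds the local goal of 25 per year |
| Six sites, 20-25 each | 120-150 | No site number is stated |

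Each matches the upper end and falls 5 short at the lower end. The first two conflict with other text; the third rests on a number the protocol does not give.

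**Step 3: can 125-150 be derived from a power formula?** No, because none of the inputs is given.

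**Step 4: what does the difference mean for precision?** These figures rest on assumptions that are not in the protocol: two-sided alpha 0.05, 80% power, and a goal-attainment rate of 60% chosen for illustration. The detectable standardized paired change solves the noncentral t power equation with n - 1 degrees of freedom and noncentrality d x sqrt(n). The 95% half-width is 1.96 x sqrt(0.6 x 0.4 / n).

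| n | Detectable change (SD) | Half-width (points) |
|---|---|---|
| 60 | 0.368 | 12.4 |
| 75 | 0.328 | 11.1 |
| 125 | 0.253 | 8.6 |
| 150 | 0.230 | 7.8 |

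Halving the sample widens both measures by a factor of about sqrt(2) = 1.41.

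**The case against.** The strongest reply is that three sites is an inference. The phrase about two other schools stands in a sentence on presenting results, and sections 3.1 and 3.2 leave room for more sites. With six sites, 28.2 would very nearly add up. This stands. A reader might infer that 125-150 cannot be reached; the documents do not support that, because they never fix the number of sites.

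A second reply is that the local figures need not clash. With one distribution year, 25 per year gives 25 participants, the top of 28.2's range, and the two years could include follow-up. That is a possible reading, but the text does not say so. It also leaves 60-75 at three sites, so it does not rescue the total.

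A third concerns feasibility. A reader might set the goal of 20-25 against 20-25 pregnancies a year and infer that nearly every pregnant trainee would have to enrol. Section 8.1 allows the number to double at most, to 40-50. At that upper bound the share needed in one year is 20/50 = 40% to 25/40 = 62.5%. Nor can the local pregnancy rate be carried over to the other schools, whose size is not given. No conclusion about achievable uptake is drawn here.

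Finally, this is a single-arm, minimal-risk and largely descriptive study with no stated target effect. A reader might infer that 60-75 is underpowered. Nothing in the protocol shows that.

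**Conclusion.** The inconsistency holds. As written, the per-site goal of 20-25 over two years and the total of 125-150 agree only with about 5 to 8 sites. The only inferable count gives 60-75, about half. The per-year reading that comes close at three sites contradicts both 28.2 and the one-year distribution window. The statement of sufficiency has no stated basis.

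If 60-75 is the real target, the detectable paired change is about 0.33-0.37 SD rather than 0.23-0.25 SD, and the half-width for a 60% attainment rate is about 11 to 12 points rather than 8 to 9. These sizes depend on the inferred three sites and on the assumed alpha, power and rate. The finding is that the figures do not reconcile; it does not show that the total is unattainable or that the analyses would fail.

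**What to change.** In sections 5.1, 8.1 and 28.2, state one consistent set of figures: number of sites, per-site goal with its time base, accrual window and resulting total.

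- If three sites and 20-25 per site are meant, restate the total as 60-75.
- If 125-150 is meant, state the sites or the accrual period that deliver it, and align the distribution window in 2.1 and 5.1.
- Give the local goal in 8.1 on the same time base as 28.2.

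Replace the claim of sufficiency with the precision at the restated total and the assumptions behind it. At 60-75, for example, this is a detectable paired change of about 0.33-0.37 SD (80% power, two-sided 0.05) and about +/-11 to 12 points for an assumed 60% goal-attainment rate. At 125-150 it is 0.23-0.25 SD and about +/-8 to 9 points.

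The cost is wording only, and no extra participants are needed. The downside is that the stated size and precision may become less favourable.
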